12.8.5 Physical Examinations, ECGs, and other Observations Related to Safety

12.8.5.1 Physical examination: Weight and BMI

Weight is planned to be measured at Screening, Visit 2, Visit 4 and Visit 6 (early withdrawal).

Based on the SAF weight and BMI (as defined in Section 10.12) observed and change from baseline values (Visit 4, Visit 6 and last on-treatment assessment (as defined in Section 10.2.4)) will be summarized by treatment arm during the 12-week on-treatment period.

The number and percentage of patients meeting a clinically significant change in weight (as defined in Table 12.8-3) at any time during the 12-week on-treatment period will be summarized by treatment arm. All measurements (scheduled or unscheduled) will be used to determine if any abnormality criteria is met.

Table 12.8-3 Weight Abnormality Criteria

Weight criteria	Abnormality criteria	
Weight (kg)	≥ 7% increase from baseline	
	≥ 7% decrease from baseline	

Weight and BMI will be listed.

12.8.5.2 Electrocardiograms

Based on the SAF, 12-lead ECG parameters (Heart rate (beats/min), PR interval (msec), QRS duration (msec), QTc B interval (Bazett's formula) (msec), QTcF (Fridericia's formula) and QT interval (msec) will be summarized by treatment arm.

ECG results will be summarized for continuous variables and will be presented for the absolute result and change from baseline values (Visit 4, Visit 6 and last on-treatment value (as defined in Section 10.2.4)) by treatment arm for the safety population.

The number and percentage of patient with any abnormal QTcF values or any other clinically significant ECG abnormality (as defined in Table 12.8-4) at baseline and within each subsequent measures performed during the 12-week on-treatment period will be summarized by treatment arm within the SAF.

Interpretation of All ECG results will be listed. Furthermore, any patients fulfilling at least one ECG abnormality criteria (as described in Table 12.8-4) or having at least one abnormal ECG assessed as significant by the investigator will be listed presenting all their ECG information.

Table 12.8-4 ECG Abnormality Criteria

ECG criteria	Abnormality criteria
QTcF interval prolongation*	> 450 msec
	> 480 msec
	> 500 msec
Change from baseline in QTcF interval*	> 30 msec increase from baseline
	> 60 msec increase from baseline
PR interval	< 120 msec
	> 200 msec
QRS complex	< 80 msec
	> 120 msec
HR	< 60 bpm
	> 100 bpm

*Abnormal QTcF interval categories as defined in ICH Guidelines E14

12.8.5.3 Columbia-Suicide Severity Rating Scale

The Columbia-Suicide Severity Rating Scale (C-SSRS) is a patient questionnaire that evaluates suicidal ideation and behaviors. In this study, the C-SSRS is assessed at Screening using the "Baseline" version and at subsequent timepoints using the "Since Last Visit" version.

The C-SSRS questionnaire is planned to be administered by the investigator (or designee) at Screening, Visit 2, Visit 3, Visit 4, Visit 5 and Visit 6.

Derived parameters are presented in Section 10.25.

On-treatment assessment

The number and percentage of patients who have answer "Yes" to each of the 5 suicidal ideation subtypes and each of the 5 suicidal behavior subtypes along with the number and percentage of patients presenting:

- A suicidal ideation
- A suicidal behavior
- A suicidal ideation or behavior
- A self-injurious behavior without suicidal intent.

will be summarized at baseline, for each scheduled on-treatment timepoint, for the 12-week on-treatment period and for last on-treatment assessment by treatment arm.

Shift table from baseline to maximal suicidal ideation score as well as a shift table for change in category (no suicidal ideation or behavior, suicidal ideation [without suicidal behavior], suicidal behavior) will also be summarized by treatment arm for patients having a baseline and at least 1 post baseline on-treatment assessment.

The number and percentage of patients presenting a suicide-related treatment-emergent events:

- A treatment emergent suicidal ideation (without suicidal behavior) compared to recent history
- A treatment emergent serious suicidal ideation compared to recent history
- An emergence of serious suicidal ideation compared to recent history
- An emergence of suicidal behavior compared to all prior history

will be summarized by treatment arm for the 12-week on-treatment period.

Observed and change from baseline in suicidal ideation score and in suicidal intensity rating score will be summarized at baseline and for each scheduled on-treatment timepoint, for the last on-treatment assessment (as defined in Section 10.2.4) and for the worst on-treatment score by treatment arm using n, mean, median, SD, Q1, Q3, min and max.

Cumulative distribution function on change from baseline to last on-treatment value and to worst ontreatment value will be plotted by treatment arm for each score. This will be displayed as increasing CDFs.

For patients with any post-baseline suicidal ideation or suicidal behavior, listings will be prepared including all C-SSRS scores for these patients.

12.8.5.4 Drug of abuse

Drug of abuse screen (including THC) is planned to be collected at Screening and Visit 2 whereas blood THC test is planned to be performed at Screening.

A by-patient listing presenting all THC measures along with urinary drug screen results will also be provided.

12.8.5.5 Pregnancies

Any reported positive pregnancy results or reported pregnancies will be listed.

12.8.5.6 Examination of oral mucosa

Based on the SAF, results of oral mucosa examination (normal, abnormal NCS and abnormal CS) will be described by treatment arm according to baseline status.

Each patient presenting at least one abnormal assessment will be listed.

12.8.5.7 Covid-19 Impact

The impact of COVID-19 on each visit will be summarized by treatment arm and a by-patient listing presenting patients impacted by COVID-19 during the conduct of the trial will be provided.

12.8.6 Monitoring of Drug Abuse Liability

Using the Potential Misuse, abuse and diversion drug event reporting System (MADDERS) "Site classification form" as reported in EDC, a summary of patients triggered for potential abuse-related adverse events will be provided by Visit (Visit 3 (titration phase), Visit 4, Visit 5 and Visit 6), for the maintenance phase (Visit 4, Visit 5 and Visit 6) and for the 12-Week on-treatment period using the SAF during the 12-week on-treatment period.

The summary will present

- The number of adjudicated events
- The number and percentage of patients with at least one adjudicated event
- The number of adjudicated events related to IMP
- The number and percentage of patients with at least one trigger event related to IMP
- The number and percentage of patients by category of type of event:
 - Tampering
 - Withdrawal
 - Addiction related indication
 - Diversion
 - Overdose

As reported by site personnel.

This summary will be repeated based on the final adjudication assessment.

Furthermore, the number and percentage of patients with at least

- one supplemental drug accountability form (MADDERS) completed
- one supplemental adverse event form (MADDERS) completed

will also be summarized by treatment arm.

The MADDERS medication use survey is a 6-item questionnaire, the 1st item includes 3 additional subitems and the 4th item has 2 parts. Each item/sub-item is being scored as "Never", "Seldom", "Sometimes" and "Often". The questionnaire is taken at end of treatment visit. Each item will be summarized by treatment arm.

Patient wise listings of the events with respect to site/investigator classification and adjudication classification will be presented.

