# 9.2.15.4 Medication Use Survey

This form consists of 18 questions regarding the use of the IMP. The trained investigator or trial coordinator will complete this survey as an interview with the patient at the End of Treatment Visit or Withdrawal Visit (Visit 6).

The MUS will be completed for all patients in the trial and not only those who have reported a triggering AE or drug accountability discrepancy, although only those with triggering AEs/drug accountability events will be adjudicated for abuse potential (see Section 9.2.18).

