#### SPONSOR: GW PHARMA LIMITED

# 10 WITHDRAWAL

In accordance with the Declaration of Helsinki, the ICH Harmonised Guideline: Integrated Addendum to ICH E6(R1): Guideline for GCP E6(R2), the US FDA regulations relating to GCP and clinical trials, the EU Clinical Trials Directive, the EU GCP Directive, and/or other applicable regulations, a patient has the right to withdraw from the trial at any time and for any reason, with no obligation to provide a reason, and without prejudice to his or her future medical care by the physician or at the institution.

The patient must be withdrawn from the trial if any of the following apply:

- Administrative decision by the investigator, GW, or a regulatory authority
- Withdrawal of patient consent
- Lost to follow-up

The patient must cease IMP and should remain in the trial if any of the following apply:

- Pregnancy
- Protocol deviation that is considered to potentially compromise the safety of the patient
- Suicidal behavior, or suicidal ideation score of 4 or 5 during the treatment period, as evaluated with the C-SSRS
- ALT or AST  $> 3 \times$  ULN with the appearance of fatigue, nausea, vomiting, right upper quadrant pain or tenderness, fever, rash, and/or eosinophilia (> 5%)
- ALT or AST  $> 5 \times ULN$
- ALT or AST > 3 × ULN and (total bilirubin [TBL] > 2 × ULN or international normalized ratio [INR] > 1.5)
- Any prohibited medication after Visit 1

The patient may be required to cease IMP at the discretion of the investigator and should remain in the trial for any of the following reasons:

- Did not meet eligibility criteria
- Patient noncompliance
- AE (including clinically significant laboratory result) that, in the opinion of the investigator, would compromise the continued safe participation of the patient in the trial
- Any evidence of drug abuse or diversion

- Disease progression (defined as a relapse of MS requiring a change in treatment)
- A positive COVID-19 test result after randomization

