10.2.4 Reporting of Longitudinal Safety Assessments

Physical examination, serum urine pregnancy test, dipstick urinalysis, examination of oral mucosa, vital signs, body weight, 12-lead ECG, clinical laboratory blood sampling, C-SSRS, MUS will be summarized using the nominal visit. In case of repeat assessments, the original assessment will be used in summaries, but all assessments will be listed.

For patients that discontinued IMP early but remained on study, assessments taken after IMP End Date will be assigned to the Follow-up visit, as long as they are within 30 days of IMP End Date.

For examination of oral mucosa, vital signs, body weight, 12-lead ECG, clinical laboratory blood sampling and C-SSRS the last on-treatment assessment will also be identified. The last on-treatment assessment is defined as the last scheduled assessment prior to IMP End Date, only assessments after the IMP Start Date will be considered (see Section 10.1 for source of dates).

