12.8 Safety Analyses

The safety analyses will be conducted during the 12-week on-treatment period (as defined in Section 10.2.2). All safety analysis will be performed by actual treatment arm (as defined in Section 9.4.1) using the SAF.

Some analyses of adverse events and laboratory parameters will assess the potential impact of IMP among the subgroups presented in Table 9.3-3.

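### The SAP's visit and window rules for off-treatment assessments relabel, or exclude from the by-arm summary, the one Medication Use Survey of patients who stop IMP early but stay in the trial

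*SAP*

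**What the plan says.** Protocol 9.2.15.4 describes MUS as an interview held at the End of Treatment or Withdrawal Visit (Visit 6). The schedule of assessments shows it at no other visit. The intended coverage is complete: "The MUS will be completed for all patients in the trial".

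SAP 12.8.6 plans a by-arm tabulation: "The questionnaire is taken at end of treatment visit. Each item will be summarized by treatment arm".

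Three SAP rules decide which surveys reach that tabulation:

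- SAP 10.2.4 puts MUS under its visit convention: "clinical laboratory blood sampling, C-SSRS, MUS will be summarized using the nominal visit". For patients who discontinued IMP early but remained on study, it adds that "assessments taken after IMP End Date will be assigned to the Follow-up visit, as long as they are within 30 days" of that date. It makes no exception for MUS.
- SAP 12.8 sets the scope for all safety output: "The safety analyses will be conducted during the 12-week on-treatment period".
- SAP 10.2.2 ends that period, for safety assessments, 30 days after IMP End Date.

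Protocol 4.1 and 9.1.4 ask patients who stop IMP early to keep to the original schedule, off treatment, up to Visit 6.

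On the instrument itself, Protocol 9.2.15.4 says "This form consists of 18 questions regarding the use of the IMP". SAP 12.8.6 describes a 6-item questionnaire in which the first item has three additional sub-items and the fourth has two parts. SAP 6.2 reports no change from the protocol.

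**The concern.** Moving vital signs or laboratory values taken after the last dose to a follow-up category is sensible, because those values describe the patient off drug. MUS looks back over how IMP was used. Its content does not become off-treatment data because the interview took place some weeks after the last spray.

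MUS also lacks the safeguard given to most of its neighbours. For oral mucosa, vital signs, weight, ECG, laboratory tests and C-SSRS, SAP 10.2.4 also identifies a last on-treatment assessment. MUS is not in that list and is scheduled once per patient, so nothing can replace a survey that is moved or excluded.

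The patients affected are not a random subset. Protocol section 10 includes "Any evidence of drug abuse or diversion" among the reasons for which the investigator may stop IMP while the patient remains in the trial, together with noncompliance and adverse events. If early stopping differs between arms, the surveys left in the table differ between arms too. The point is still live after early termination: the SAP addendum keeps section 12.8.6 and removes only the summary of triggered events, so the MUS table is one of the few by-arm abuse-liability outputs that remain.

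**Working it through.** The plan states no figure for this point, so there is nothing to reproduce. The check is a trace through the rules with day arithmetic.

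**Inputs.** Visit 6 is on Day 85 ± 7, that is Day 78 to Day 92 (Protocol 4.1, SAP 8.1). The relabelling limit is 30 days after IMP End Date (SAP 10.2.4). The safety window closes 30 days after IMP End Date (SAP 10.2.2, applied through SAP 12.8). MUS is done at Visit 6 only.

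**Rule.** For a patient who stops early and stays, let V be the Visit 6 day and E the IMP end day. The lag is V − E.

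- Lag of 1 to 30 days (E ≥ V − 30): relabelled to Follow-up, inside the safety window.
- Lag over 30 days (E < V − 30): no Follow-up assignment, outside the safety window.

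| Visit 6 day | V − 30 | IMP end days relabelled | IMP end days outside the window |
|---|---|---|---|
| 78 | 48 | 48–77 | 1–47 |
| 85 | 55 | 55–84 | 1–54 |
| 92 | 62 | 62–91 | 1–61 |

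In neither band does 10.2.4, together with the safety window, leave the Visit 6 survey in an end-of-treatment summary. The first band is moved; the second is excluded.

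**Size.** Let f be the share of an arm whose surveys are excluded, r_s their rate of a given response, and r_o the rate among the rest. The full rate is f·r_s + (1 − f)·r_o and the table shows r_o, so the understatement is f·(r_s − r_o). None of these three quantities is in the documents. The following values are assumptions only:

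- f = 20%, r_s = 15%, r_o = 3%: 0.20 × 0.12 = 2.4 points (5.4% against 3.0%).
- f = 5%, r_s = 10%, r_o = 3%: 0.05 × 0.07 = 0.35 points.
- f = 25%, r_s = 30%, r_o = 3%: 0.25 × 0.27 = 6.75 points.

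Here f must count only surveys that actually leave the table. If relabelled surveys stay in, f is limited to patients with a lag over 30 days. For scale, f of 5% to 20% would be about 11 to 45 of the planned 223 per arm (223 × 0.05 = 11.2; 223 × 0.20 = 44.6). Enrollment stopped short of the plan, so these counts are illustrative too.

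**Question count.** The SAP description gives 6 items + 3 sub-items + 1 extra part = 10 responses, against 18 questions in the protocol.

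**The case against.** Several arguments limit the point.

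- **A relabelled survey need not be lost.** SAP 12.8.6 asks for the triggered-event summary by visit but for the MUS items only by arm. A table with no visit dimension would keep a survey done within 30 days of IMP End Date, which is also inside the safety window. This stands: for that band the outcome depends on a layout that the SAP does not give.
- **No sentence states the exclusion beyond 30 days.** SAP 10.2.4 does not say what happens to later assessments, and its default is the nominal visit. The MUS paragraph does not repeat the on-treatment restriction. It is true that three sections must be combined. But 12.8.6 is a subsection of 12.8, whose window covers all safety analyses, so keeping the nominal Visit 6 label would not bring a later survey back in.
- **Some early stoppers may be interviewed sooner.** Protocol 12.7 requires an end-of-treatment assessment when IMP is stopped for an adverse event. A survey done then, on IMP End Date, would not be moved. The protocol does not say that this assessment includes MUS.
- **Patients who leave at an Early Withdrawal Visit are outside the relabelling rule**, because they did not remain on study.

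A reader might infer that a survey excluded from the table is reported nowhere. The documents do not support that. SAP 10.2.4 says that all assessments are listed (in its sentence on repeats), although 12.8.6 names no MUS listing, and under Protocol 9.2.18.4 the adjudication committee reviews MUS for triggered cases. A reader might also infer that the excluded patients are those most likely to report misuse. The reasons for stopping also include pregnancy, liver enzyme elevations, prohibited medication, MS relapse and COVID-19, so informative loss is plausible but not shown.

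**Conclusion.** The point holds for the by-arm MUS summary. Followed as written, the SAP excludes the only scheduled survey of a patient who stops IMP before about Day 55 and stays to a Day 85 Visit 6 (Day 48 to Day 62 across the visit window). It relabels the survey of a patient who stops later, with an outcome that depends on table layout. Both conflict with the protocol's intent that MUS cover every patient. The conclusion assumes that early stoppers keep to the original schedule, as the protocol asks, and that the SAP 12.8 window applies to MUS as to other safety output.

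It would go too far to say that every early stopper's survey is lost, or to attach a bias to the table. The percentage-point range above is only as good as its assumed rates, and the true size is unknown. Collection of the survey is not affected, and neither is any hypothesis test. This is a modest gap in a descriptive safety output.

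The difference in question counts is a separate inconsistency. A reader might conclude that 8 questions would go untabulated (18 − 10). The form is not in the documents, and nothing shows which count is right or whether some questions use another response format. Only the mismatch is established.

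**What to change.** 1. In SAP 10.2.4, exempt MUS from the rule that reassigns assessments made after IMP End Date.
2. In SAP 12.8.6, state that each patient's one MUS, from Visit 6 or the Early Withdrawal Visit, is summarized by arm in the Safety Analysis Set regardless of the time since IMP End Date.
3. Check the number of MUS questions against the eCRF, align the protocol and SAP descriptions, and tabulate every question collected.

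The cost is a few sentences in the SAP or its addendum and one check of the form. No new data are needed.

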14.0 Glossary of Abbreviations

Glossary of Abbreviations:		
11-COOH-THC	11-nor-9-carboxy- Δ^9 -tetrahydrocannabinol	
11-OH-THC	11-hydroxy-Δ ⁹ -tetrahydrocannabinol	
7-COOH-CBD	7-carboxy-cannabidiol	
7-OH-CBD	7-hydroxy-cannabidiol	
ADaM	Analysis dataset model	
ADL	Activity of daily living	
AE	Adverse event	
ALP	Alkaline phosphatase	
ALT	Alanine aminotransferase	
ANCOVA	Analysis of covariance	
ATC	Anatomic therapeutic class	
AR(1)	First order autoregressive	
AST	Aspartate aminotransferase	
BDZ	Benzodiazepine	
BLQ	Below limit of quantification	
BMI	Body mass index	
BP	Blood pressure	
BP	Bodily pain	
bpm	Beats per minutes	
CBD	Cannabidiol	
CDF	Cumulative distribution function	
CFB	Change from baseline	
CI	Confidence interval	
COVID-19	Coronavirus disease 2019	
CRF	Case report form	
CS	Compound symmetric	
CS	Clinically significant	
CSR	Clinical study report	
C-SSRS	Columbia-suicide severity rating scale	
CTCAE	Common terminology criteria for adverse events	
CV	Coefficient of variation	
СҮР	Cytochrome 450	

Glossary of Abbreviations:	
D	Day
DBP	Diastolic blood pressure
DILI	Drug-induced liver injury
DMD	Disease modifying drug
ECG	12-lead electrocardiogram
eCRF	Electronic case report form
EDC	Electronic data capture
eDiary	Electronic diary
EDSS	Expanded disability status scale
eGFR	Estimated glomerular filtration rate
ELISA	Enzyme-linked immunosorbent assay
FAS	Full analysis set
FU	Follow-up
FUAS	Follow-up analysis set
GGT	Gamma-glutamyl transferase
GH	General health
GW	GW Pharma Ltd / GW Pharma Limited
Н	Hour
HR	Heart rate
HRQOL	health-related quality of life
hrs	hours
НТ	Health transition
ICH	International Council for Harmonization
IMP	Investigational medicinal product
INR	International normalized ratio
IPD	Important protocol deviation
IRT	Interactive response technology
KR	Kenward-Roger
LLN	Lower Limit of Normal
LOCF	Last observation carried forward
LS mean	Least square mean
М	Month
MADDERS	Misuse, abuse and diversion drug event reporting system
MAR	Missing at random

Glossary of Abbreviation	ons:		
MAS	Modified Ashworth scale		
Max	Maximum		
МСМС	Markov chain Monte Carlo		
MCS	Mental component summary		
ME	Most extreme		
MedDRA	Medical Dictionary for Regulatory Activities		
МН	Mental health		
МНР	Mobile health platform		
МІ	Multiple imputation		
Min	Minimum		
MMRM	Mixed model repeated measures		
MNAR	Missing not at random		
MS	Multiple sclerosis		
MSS	Multiple sclerosis spasticity		
MSSS-88	Multiple Sclerosis Spasticity Scale		
MUS	Medication Use Survey		
NA	Not applicable		
NCS	Not clinically significant		
NRS	Numerical rating scale		
OR	Odds ratio		
PCS	Physical component summary		
PF	Physical functioning		
РК	Pharmacokinetics		
РММ	Pattern mixture model		
PP	Per protocol		
PR	Pulse rate		
PRN	pro re nata (As-needed)		
PRO	Patient reported outcome		
PSO	Predictive study operations		
РТ	Preferred term		
PUC	Prior use of cannabis		
Q1	First Quartile / Quartile 1		
Q3	Third Quartile / Quartile 3		
QoL	Quality of life		

Glossary of Abbreviation	ons:		
QTc B	QT corrected Bazett's formula		
QTc F	QT corrected Fridericia's formula		
RE	Role-emotional		
RP	Role-physical		
SAE	Serious adverse event		
SAF	Safety analysis set		
SAP	Statistical analysis plan		
SAT	Satterthwaite		
SBP	Systolic Blood Pressure		
SD	Standard deviation		
SDTM	Study data tabulation model		
SE	Standard error		
sec	second		
SF	Social functioning		
SF-36	36-Item short form health survey		
SI	Standard international		
SOC	System organ class		
T25FW	Timed 25-Foot Walk		
TBL	Total bilirubin		
TEAE	Treatment-emergent adverse event		
ТНС	Δ9-tetrahydrocannabinol		
TOEP	Toeplitz		
UGT	Glucuronosyltransferase		
ULN	Upper limit of normal		
UN	Unstructured		
US	United States		
USA	United States of America		
VT	Vitality		
WHO-DD	World Health Organization-Drug Dictionary		
Υ	Year		

